1.2. Research Questions

1.2.1. Is there a difference in the rate of administration for rescue opioid analgesic medications in children undergoing tonsillectomy who are administered hydromorphone as compared to fentanyl perioperatively?

1.2.2. Is there a difference in the postoperative pain score in children undergoing tonsillectomy who are administered hydromorphone as compared to fentanyl perioperatively?

1.2.3. Is there a difference in the cumulative morphine equivalents administered postoperatively in children undergoing tonsillectomy who are administered hydromorphone as compared to fentanyl perioperatively?

1.2.4. Is there a difference in post anesthesia care unit length of stay in children undergoing tonsillectomy who are administered hydromorphone as compared to fentanyl perioperatively?

1.2.5. Is there a difference in nausea or the number of vomiting episodes postoperatively and 72 hours after discharge in children undergoing tonsillectomy who are administered hydromorphone as compared to fentanyl perioperatively?

CONFIDENTIAL: This document is the intellectual property of [name] and [name], PhD. Acceptance of this document constitutes the agreement by the recipient that no unpublished information contained herein will be published or disclosed without prior written approval.

1.2.6. Is there a difference in pain scores reported by the parent 72 hours after discharge in children undergoing tonsillectomy who are administered hydromorphone as compared to fentanyl perioperatively?

1.2.7. Is there a difference in the number of desaturation events, defined as $\text{SPO}_2 < 90\%$ for 2 minutes or less than 85% for 1 minute, postoperatively in children undergoing tonsillectomy who are administered hydromorphone as compared to fentanyl perioperatively?

1.2.8. Is there a difference in the number of witnessed apneic events postoperatively or at 72 hours after discharge in children undergoing tonsillectomy who are administered hydromorphone as compared to fentanyl perioperatively?

1.2.9. Is there a difference in patient and family satisfaction with care between children undergoing tonsillectomy who are administered hydromorphone as compared to fentanyl perioperatively?

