1.3. Purpose of the Study Protocol. The proposed project will test whether there is a difference in multiple metrics of pain between patients who receive hydromorphone or those who receive fentanyl during tonsillectomy. The results of this study should inform the way anesthesiologists approach the treatment of pain following the most common pediatric surgical procedure at SLCH, and in the United States. If a difference is found, appropriate dissemination of findings could influence the universal approach taken for pain control in the most common pediatric surgery.

2. Background

2.1. Prior Literature and Studies. Tonsillectomy is the most common pediatric operation performed in the United States, with more than 500,000 tonsillectomies performed annually¹. The primary indication for tonsillectomy is childhood obstructive sleep apnea (OSA), defined by periodic, partial or complete obstruction of the upper airway during sleep. OSA is a common disorder in pediatric patients, with a prevalence of 1-3%². It is as common as childhood asthma and children with OSA often require tonsillectomy surgery to correct their OSA². As mentioned, the treatment of OSA is the primary indication for more than 75% of children undergoing tonsillectomy with or without adenoidectomy³. Unfortunately, children at high risk for OSA are three times more likely to have post-tonsillectomy respiratory complications and apneic adverse events than children at low risk for OSA^{4,5} and the rate of complications in patients with OSA post-tonsillectomy (16 –27%) is substantially increased compared to that of the general pediatric post-operative population (0 –1.3%)⁶⁻¹⁰. These complications include oxygen desaturation, hypercapnia, obstructive apneas requiring CPAP or airway instrumentation, unexpected ICU admission, and in rare cases, death. Concerns for a heightened risk of opioid induced respiratory depression make the peri-operative use of opioids in children with OSA particularly challenging and controversial.

CONFIDENTIAL: This document is the intellectual property of [name] and [name], PhD. Acceptance of this document constitutes the agreement by the recipient that no unpublished information contained herein will be published or disclosed without prior written approval.

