There is currently not a standard of practice for pain management for tonsillectomy surgery at SLCH. Published guidelines recommend decreasing opioid doses in all patients with sleep apnea, for fear of respiratory depression, however they do not give recommendations regarding the use of short vs. intermediate acting opioids¹¹. The nurses in the SLCH PACU have subjectively noted a decreased need for opioid rescue analgesia when hydromorphone is administered intraoperatively as compared to fentanyl. Additionally, a recently completed prospective study of fentanyl versus hydromorphone for pain control in patients undergoing eye muscle surgery at SLCH suggests that hydromorphone results in lower pain scores and faster PACU recovery¹². There are limited data comparing different opioids in pediatric tonsillectomy surgery published in the literature. As far as we are aware, this will be the first randomized controlled trial comparing the intermediate acting opioid hydromorphone to the shorter acting opioid fentanyl for this patient population.

2.2. Rationale for the Study. Providing safe and effective pain control is important for these patients. Subjective observations indicate that hydromorphone may provide superior pain control as compared to fentanyl. This hypothesis has not been rigorously tested. We aim to ameliorate this deficit.

3. Study Objectives

3.1. Primary Aim. The **primary aim** of our study is to compare the need for rescue opioid analgesic medication between patients receiving fentanyl and hydromorphone following adenotonsillectomy surgery. We will also compare post-operative pain scores between the two groups, and the amount of opioid pain medications administered to patients postoperatively expressed in morphine equivalents. Patients will be randomized 1:1 in the operating room to receive either fentanyl or hydromorphone during the perioperative period. We hypothesize that compared to fentanyl, the use of hydromorphone will result in lower need for rescue opioid analgesic in post-surgical recovery.

3.2. Secondary Aims. The **secondary aims** of our study are to compare pain scores, the rates of post-operative respiratory complications, PONV, and length of PACU stay between patients administered fentanyl vs. hydromorphone. We hypothesize that there will be no differences between patients who receive fentanyl and those who receive hydromorphone.

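### Section 6.2 uses a baseline factor only after a significant imbalance, which the stratified blocks of 4 in 4.9 almost rule out for recent PSG-diagnosed OSA; analyse by the randomization strata regardless

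*Combined protocol and SAP*

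**What the plan says.** **Respiratory comparisons.** Section 3.2 sets out to "compare pain scores, the rates of post-operative respiratory complications, PONV, and length of PACU stay between patients administered fentanyl vs. hydromorphone". Section 1.2.7 asks "Is there a difference in the number of desaturation events" and 1.2.8 asks "Is there a difference in the number of witnessed apneic events postoperatively or at 72 hours after discharge". All three contrast the two drug groups as wholes. The hypothesis in 3.2 is one of equality: "We hypothesize that there will be no differences between patients who receive fentanyl and those who receive hydromorphone".

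**Risk group.** Section 2.1 says that "the treatment of OSA is the primary indication for more than 75% of children undergoing tonsillectomy" and that "children at high risk for OSA are three times more likely to have post-tonsillectomy respiratory complications". It gives complication rates of 16 to 27% with OSA, and says that concerns about respiratory depression "make the peri-operative use of opioids in children with OSA particularly challenging and controversial". It adds: "Published guidelines recommend decreasing opioid doses in all patients with sleep apnea, for fear of respiratory depression".

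**Randomization.** Section 4.9 allocates 1:1 in blocks of 4 within strata formed by three age groups (2-7, 8-12, 13-15) and by OSA diagnosed on a sleep study in the past year. That makes six cells.

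**Analysis.** Section 6.2 compares the arms at baseline at p<0.05 and brings in multivariate adjustment only where a difference is significant. It does not mention the stratification factors. No section plans a stratified analysis or a respiratory result by OSA status.

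**The concern.** A significance trigger for adjustment is doubtful in general. Here it also conflicts with the design. Stratified blocks exist to keep the arms alike on PSG-OSA, and the better they work, the more surely 6.2 leaves PSG-OSA out of the analysis. The trial would stratify on the condition that it names as the respiratory hazard and then analyse as though it had not.

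Two things are at stake, both modest. An unstratified test after stratified randomization carries between-stratum variation in its standard error that the design has already removed, so it is slightly conservative. And because 3.2 expects no difference, a non-significant overall result is the authors' own forecast. With no planned analysis that uses PSG-OSA, any look at it would be absent or post hoc.

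**Working it through.** **1. The plan's own figure.** The documents give no calculation for respiratory outcomes. The only figures to reproduce are those for rescue analgesia in 6.1, with n per arm = [1.96·√(2p̄q̄) + 0.8416·√(p₁q₁ + p₂q₂)]² / (p₁ − p₂)².
- 36% v 18%: 95 per arm, 190 in total, × 1.2 = 228, as stated.
- 50% v 25%: 58 per arm, 116 in total, × 1.2 = 139, as stated.

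This supports reading alpha as two-sided 5%. Nothing below depends on it.

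**2. Largest possible imbalance.** Only the last, incomplete block in a cell can be unbalanced, and by at most 2 children. PSG-OSA spans three age cells, so the arms can differ by at most 3 × 2 = 6 children with PSG-OSA before dropout. Each age group spans two cells, so the limit there is 4.

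**3. Does 6 reach p<0.05?** The documents do not give the PSG-OSA share, so 10 to 75% is assumed, with 150 per arm and z = (x₁ − x₂)/150 ÷ √(2p̄q̄/150).

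| Share | Counts | p |
|---|---|---|
| 10% | 18 v 12 | 0.25 |
| 20% | 33 v 27 | 0.39 |
| 30% | 48 v 42 | 0.45 |
| 50% | 78 v 72 | 0.49 |
| 75% | 115 v 109 | 0.43 |

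At 10%, for example, z = 0.04/√(2 × 0.1 × 0.9/150) = 0.04/0.0346 = 1.15. Significance needs a gap of 1.96 × 0.0346 × 150 ≈ 10 children at a 10% share and 1.96 × 0.0577 × 150 ≈ 17 at 50%. These p-values are for the expected counts and are not strict bounds, since a trial may enroll fewer PSG-OSA children than expected.

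**4. Simulated trigger.** Blocks of 4 in six cells, assumed age mix 60/30/10, 400,000 trials per share:
- 300 randomized, no dropout: fired 0 times; smallest p 0.15.
- 360 randomized (5.2), 20% random dropout: fired in 0.003 to 0.026% of trials.

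Simple randomization would fire in about 5%.

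**5. Cost of ignoring the stratum.** Overall two-proportion test against Mantel-Haenszel (MH) stratified by PSG-OSA, 150 per arm.
- *Other stratum free of OSA.* OSA rate 16 or 27% (2.1), one third of that otherwise, shares 15 to 75%. Type I error is 4.1 to 4.7% unstratified and 4.6 to 5.2% with MH. For an odds ratio of 2, MH adds about 1 to 2.5 points of power (for example 59.3% to 61.8% at a 30% share and a 27% rate).
- *Other stratum mixed.* If 75% of all children have OSA and many have had no recent sleep study, the strata resemble each other. At a 20% share the OSA fraction of the other stratum is (0.75 − 0.20)/0.80 = 0.69. With a 21.5% OSA rate its event rate is 17.0%. Over 30 such settings MH gains 0.0 to 1.9 points, and unstratified type I error is 4.6 to 5.1%.
- *Extreme contrast.* A 1.3% rate in the other stratum (30% share) gives unstratified type I error of 3.0 to 3.9% and power of 27 to 29%, against 32 to 38% with MH. Section 2.1 gives 1.3% as the top of the range for general pediatric postoperative patients, not for tonsillectomy without OSA, so this is an outer limit.

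**6. Do six cells work?** With assumed age mixes of 60/30/10 and 50/30/20 and cells as small as 1 per arm, six-cell MH has type I error of 4.8 to 5.1% and 95% interval coverage of 94.7 to 95.0% at OSA rates of 16 to 27%. At OSA rates of 2 to 10%, coverage is 94.8 to 95.6% and type I error 4.4 to 5.0%.

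**7. Precision within the PSG-OSA stratum.** Half-width = 1.96·√(2 × 0.215 × 0.785/n), no drug effect.

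| Share | n per arm | Half-width (points) |
|---|---|---|
| 10% | 15 | 29 |
| 20% | 30 | 20.8 |
| 50% | 75 | 13.1 |
| 75% | 112 | 10.8 |

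At a 20% share, the difference between strata has half-width 1.96·√(2 × 0.215 × 0.785/30 + 2 × 0.170 × 0.830/120) = 22.9 points.

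**The case against.** The strongest reply is that a trigger that never fires is doing its job. Section 6.2 adjusts for confounders, and stratified blocks stop PSG-OSA from becoming one. That stands as far as bias goes: the unstratified comparison is unbiased. It does not settle the matter, because the usual reason to analyse by randomization factors is to have a standard error that matches the design, not to remove confounding.

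Two further replies stand. The point covers only OSA diagnosed by sleep study in the past year. Section 5.3 reviews any earlier sleep study, so older results, severity or clinically suspected OSA could still differ at baseline and lead to adjustment under 6.2. Dropout that depended on both arm and OSA could also raise the trigger rate. And a table by stratum would be imprecise, comparing recent PSG-OSA with a group that may hold many untested children with OSA. A null row in it could itself mislead, so it is optional here.

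A reader might infer that the whole-group comparison would hide respiratory harm in OSA. The documents do not support that. If risk doubled in every child with OSA, with 75% affected (the indication figure in 2.1, not a trial-specific share) and a 21.5% rate, the overall excess would be 0.75 × 21.5 = 16.1 points, and the unstratified test would have about 90% power. Heavy dilution needs a harm confined to a small PSG-OSA stratum.

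**Conclusion.** The point holds as a free improvement, at the level of something to consider. As written, 6.2 in practice discards the PSG-OSA stratification factor: at most 6 children of imbalance before dropout, and a trigger rate of about 0 to 0.03% across assumed shares of 10 to 75%, given dropout unrelated to arm and OSA. The loss is small: type I error of about 4 to 5% in place of 5%, and typically 0 to 2.5 points of power. The size depends on the PSG-OSA share and on how far event rates differ between strata, neither of which the documents give.

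A reader might also infer that the trial intends to claim respiratory safety in OSA. No section makes that claim. The risk is only that a non-significant overall result is read that way.

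**What to change.** In 6.2, drop the significance trigger for the stratification factors and state that between-arm comparisons account for PSG-OSA and age group whatever the baseline tests show. Specifically:

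1. For the respiratory complication rate in 3.2, report the hydromorphone-minus-fentanyl Mantel-Haenszel risk difference, with 95% CI, in the proportion of children with at least one event. If a cell has no children in one arm, merge age groups and keep PSG-OSA.
2. For the event numbers in 1.2.7 and 1.2.8, keep the counts as the outcome and use a stratified test or a count model with both factors.
3. Optionally, add one table labelled descriptive, giving respiratory events by arm within PSG-OSA stratum. Note that its intervals are wide (about ±11 to ±29 points at assumed shares of 75% to 10%), that the other stratum is not free of OSA, and that a non-significant overall result does not show respiratory safety in OSA.

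The cost is a few sentences and at most one table, using strata already recorded at randomization, with no new patients, visits or data. Item 1 does fix a definition (at least one event per child) that 3.2 leaves open. Because 5.5 has the principal investigator watching unblinded data as they accrue, the change should be recorded before those data could influence it.

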4.2. Inclusion Criteria

- 4.2.1. Children ages 2 to 15 years old
- 4.2.2. Presenting for tonsillectomy surgery or adenotonsillectomy surgery
- 4.2.3. American Society of Anesthesiologists Physical Status (ASAPS) Classification 1, 2 or 3
- 4.2.3. The caregiver of the child must be able to provide informed consent and the child must be able to provide assent (as appropriate)

4.3. Exclusion Criteria

- 4.3.1. Additional Concurrent surgeries, exclusive of myringotomy tubes, minor oral/nasal procedures (e.g. frenulectomy), and endoscopic procedures
- 4.3.2. Revision tonsillectomy or revision adenotonsillectomy surgery
- 4.3.3. Known pregnancy
- 4.3.4. Any condition which would make the participant, in the opinion of the investigator, unsuitable for the study

4.4. Ethical Considerations. All patients will receive pain medication as well as medication to control for postoperative nausea and vomiting as per routine care at SLCH. The attending anesthesiologist will accompany the child to the PACU, and rescue drugs will be available if additional pain medication is needed or if there is concern for respiratory distress. Both medications (hydromorphone and fentanyl) to be compared are standard of care analgesics at SLCH and on formulary.

4.5. Risks and Benefits. We do not know if patients will benefit from the intervention. For future patients, it is anticipated that investigators may be able to determine whether one of the pain medications has a better potential to reduce the need for rescue analgesia without a concomitant increase in side effect following tonsillectomy surgery. There is a possibility that parents may feel uncomfortable answering some items on the questionnaires.

4.6. Early Withdrawal of Subjects. Patients may be withdrawn from the study if during surgery an additional procedure is required or if the lead study physician ([name]) determines it is not in the best interest of the patient to continue in the study. Caregivers may decide to withdraw their child from the study at any time without penalty. Withdrawn children will be replaced with a new subject to maintain a consistent number of enrolled patients in each group.

4.7. Study Medications, Administration, and Blood Plasma Concentration Measurements

CONFIDENTIAL: This document is the intellectual property of [name] and [name], PhD. Acceptance of this document constitutes the agreement by the recipient that no unpublished information contained herein will be published or disclosed without prior written approval.

4.7.1. Hydromorphone. Hydromorphone hydrochloride (4,5a-epoxy-3-hydroxy-17-methylmorphinan-6-one hydrochloride) is a hydrogenated ketone of morphine. Hydromorphone hydrochloride is a pure opioid agonist with the principal therapeutic activity of analgesia. A significant feature of the analgesia is that it can occur without loss of consciousness. Opioid analgesics also suppress the cough reflex and may cause respiratory depression, mood changes, mental clouding, euphoria, dysphoria, nausea, vomiting and electroencephalographic changes. Many of the effects described above are common to the class of mu-opioid analgesics, which includes morphine, oxycodone, hydrocodone, codeine, and fentanyl. Hydromorphone has been most extensively studied in adults, however it is commonly used in pediatrics both in the perioperative and inpatient settings. At therapeutic plasma levels in adults, hydromorphone is approximately 8-19% bound to plasma proteins. Hydromorphone is extensively metabolized via glucuronidation in the liver, with greater than 95% of the dose metabolized to hydromorphone-3-glucuronide along with minor amounts of 6-hydroxy reduction metabolites. Only a small amount of the hydromorphone dose is excreted unchanged in the urine. Most of the dose is excreted as hydromorphone-3-glucuronide along with minor amounts of 6- hydroxy reduction metabolites. The terminal elimination half-life of hydromorphone after an intravenous dose is about 2.3 hours in adult FDA studies¹³.

4.7.2. Fentanyl. Fentanyl citrate (N-1-phenethyl-4-piperidyl propionanilide citrate) is a potent opioid agonist with principal therapeutic activities of analgesia and sedation. As with other potent opioid agonists, the most common serious adverse reactions reported to occur with fentanyl are respiratory depression, apnea, rigidity, and bradycardia; if these remain untreated, respiratory arrest, circulatory depression, or cardiac arrest could occur. Other adverse reactions that have been reported are hypertension, hypotension, dizziness, blurred vision, nausea, emesis, diaphoresis, pruritus, urticaria, laryngospasm and anaphylaxis. Like hydromorphone, fentanyl has been most extensively studied in adults but is commonly used in the pediatric patient population, especially in the perioperative period. In adults, the pharmacokinetics of fentanyl can be described as a three-compartment model, with a distribution time of 1.7 minutes, redistribution of 13 minutes and a terminal elimination half-life of 219 minutes. Fentanyl plasma protein binding capacity decreases with increasing ionization of the drug. It accumulates in skeletal muscle and fat, and is released slowly into the blood. Fentanyl, which is primarily metabolized by the liver, demonstrates a high first pass clearance and releases approximately 75% of an intravenous dose in urine, mostly as metabolites with less than 10% representing the unchanged drug. Approximately 9% of the dose is recovered in the feces, primarily as metabolites. The onset of action of fentanyl is almost immediate when the drug is given intravenously; however, the maximal analgesic and respiratory depressant effect may not be noted for several minutes¹⁴.

4.7.3. Administration. The study will be conducted in the operating room and in the PACU. In the operating room, patients will receive a general anesthetic with an endotracheal tube directed by the attending anesthesiologist as per routine care at SLCH. Standard ASA monitors, which include pulse oximetry, non-invasive blood pressure monitoring, telemetry, heart rate monitoring, and end tidal CO₂ and oxygen monitoring will be

CONFIDENTIAL: This document is the intellectual property of [name] and [name], PhD. Acceptance of this document constitutes the agreement by the recipient that no unpublished information contained herein will be published or disclosed without prior written approval.

connected to the patient as per standard of care. Patients will be randomized to receive either hydromorphone or fentanyl in the operating room determined by opening a sealed protocol envelope. Administration and dosing of the randomized opioid to each case will be under the direction of the primary anesthesia team under the direction of the pediatric anesthesiologist caring for the child. In addition to the randomized opioid, patients will receive non-opioid analgesics and PONV prophylaxis as per routine care at SLCH. Blinding will be achieved using syringes prepared by SLCH investigational pharmacy.

4.7.4 Optional opioid Plasma Concentration Assessments. Approximately 3 mls of whole blood will be collected from patients at three time points: 1) within 10 minutes of administration of study drug, 2) within 10 minutes of PACU arrival, and 3) within 10 minutes of PACU discharge. Blood samples will be collected through an additional IV line placed in the surgical suite after anesthesia is given. Opioid (hydromorphone or fentanyl) blood levels will be measured using mass spectrometry. This type of analysis does not require *apriori* knowledge of the medication administered and will maintain the masking protocol. A Population Pharmacokinetic Analysis will be performed. The patient may decline to participate in the blood draw component of the study and remain in the study for data collection relating to the primary endpoint. Additionally, failed or missed blood draws in individual patients will not adversely affect the population analysis.

4.8. Treatment Regimen. Patients will receive a general anesthetic as per the standard of care at SLCH. Analgesia will include opioids and non-opioid adjuvants for pain in addition to anti-emetics per routine care at SLCH. Airway maintenance will be via an endotracheal tube supervised by the anesthesiologist responsible for the care of the patient in the operating room.

4.9. Method for Assigning Subjects to Treatment Groups. Patients will be randomized to either hydromorphone or fentanyl in the preoperative area prior to presenting to the operating room by investigational pharmacy staff. Randomization will be 1:1 in blocks of 4 within strata. Stratification will be done by age group (2-7, 8-12, and 13-15), and OSA diagnosed using sleep polysomnography within the last year.

4.10. Preparation of the Study Drugs. Equi-analgesic dose tables poorly accommodate differences in rapid redistribution between drugs. Establishing a definitive therapeutic equivalence between hydromorphone and fentanyl for the patient population, type of stimulus, and duration of procedure is challenging *a priori*. Previous data gathered at SLCH and clinical expertise guide our dosing choices. Hydromorphone, when utilized as the sole opiate intraoperatively is dosed with median 10 ± 4 mcg/kg with 16 mcg/kg as the 80th percentile, and fentanyl is dosed with median 0.9 ± 0.5 mcg/kg, with 1.5 mcg/kg at the 80th percentile. We will use these current medians to guide our dosing. We will initiate medication dosing of patients with hydromorphone 10 mcg/kg, and fentanyl 1 mcg/kg. Conveniently, formulary preparation of hydromorphone is at 500 mcg / ml and fentanyl at 50 mcg/ml. Thus, blinding should be achievable as the same volume of medication (ml/kg) can be safely administered for each drug.

CONFIDENTIAL: This document is the intellectual property of [name] and [name], PhD. Acceptance of this document constitutes the agreement by the recipient that no unpublished information contained herein will be published or disclosed without prior written approval.

Regarding feasibility, we conducted an informal survey of attending anesthesiologists at SLCH. We had an approximately 50% response rate and all were willing to give these two drugs at the proposed doses in a blinded fashion.

5. Study Procedures

5.1. Screening for Eligibility. The patient's medical record will be screened for: age of child, type of surgical procedure planned, history of previous surgery, classification score for anesthesia, whether child is in custody of a legal caregiver, and ability to consent/assent to the study.

5.2. Enrollment. The surgery schedule at SLCH is posted in advance therefore it is straightforward to determine daily if there are eligible subjects to approach for inclusion. The patient's medical history is available to screen for eligibility criteria prior to asking if they would be interested in participating. The day prior to the surgery, a nurse may contact the family to deliver preoperative instructions. At this time, the family may be told a study is being conducted and given details on possible participation. Additionally, the research team will identify potential patients on the day of surgery that may qualify for the study. A member of the research team will then approach the family in the private room in the surgical preoperative area to discuss the study and review the consent form. The study group will consist of 300 patients who are presenting for tonsillectomy surgery or tonsillectomy and adenoidectomy surgery. Enrollment completion will be achieved once consent for up to 360 patients is obtained, assuming a 20% drop-out rate from the study, with an end goal of 300 patients.

5.3. Schedule of Measurements. Consenting families will be evaluated with the YPAS-m scale prior to surgery. At the time consent is obtained, parents will also be asked to complete a brief demographic data form. Any preoperative sleep studies (also known as polysomnograms) that subjects had previously received will be reviewed. After surgery, the post-operative recovery nurse will evaluate the patient's pain using rFLACC scale on arrival to the Post Anesthesia Care Unit (PACU), and then every five minutes during the patient's stay. This is standard of care.

After transferring from Phase I recovery, a member of the research team will continue to evaluate patient's pain using the same scale on arrival and before discharge. The patient's level of pain (rFLACC) and need for any additional analgesic medications will also be evaluated. rFLACC is standard of care at SLCH and all personnel are well versed in its application. After discharge, the patient will receive a telephone call or text at 24 hours after surgery to evaluate post-operative nausea and vomiting and the level of pain at home. The need for additional pain medication will also be assessed. This is standard of care at SLCH and performed for all patients who are discharged the day of surgery, regardless of type of surgery. Respiratory events will be assessed initially using SpO₂ monitoring immediately after arrival to the PACU, followed by clinical assessment after PACU discharge. Postoperative nausea and vomiting is assessed using observation and patient verbalization.

CONFIDENTIAL: This document is the intellectual property of [name] and [name], PhD. Acceptance of this document constitutes the agreement by the recipient that no unpublished information contained herein will be published or disclosed without prior written approval.

Patient and family satisfaction with care will be assessed using a survey on postoperative day 3, as well as the validated NIH PROMIS questionnaires for Pediatric Self-Report (ages 8-17) and Parent Proxy Report (ages 5-17). We will use the following NIH PROMIS questionnaires: Pain Behavior, Pain Interference, and Pain Quality. PROMIS questionnaires will be sent to patients via e-mail through the REDCap server on postoperative day 7 (\pm 1 day).

5.4. Safety and Compliance Monitoring. All patients will be monitored by an anesthesiologist for the first 5 minutes in the PACU and then every 5 minutes by a registered nurse until discharged from the PACU to the Same Day Surgery unit. Monitoring is continuous until the patient recovers from anesthesia and then every 5 minutes x3, then every 15 minutes until PACU discharge. The same tool, the rFLACC, is used throughout the hospitalization to assess pain. Postoperative nausea and vomiting is assessed using observation and patient verbalization.

5.5. Medical Monitoring. The PI will be monitoring all unblinded data as it is collected throughout the study and share the information with the anesthesiologists and the surgeons. In general, the Department of Anesthesiology has developed a specific set of Standard Operating Procedures (SOPs) for clinical research. All individuals working on study are required to read and be familiar with and compliant with the SOPs. The SOPs are in part developed from and are compliant with the Institutional Guidelines, including those for a) Interactions with the Washington University Human Subjects Review Committee, b) Informed Consent Development and Implementation, c) Subject Recruitment and Screening, d) Subject Management While on Study, e) Adverse Event Reporting. The potential risks of this study are attributable to the use of opioids in the perioperative period.

As already per routine care at SLCH, there will always be a non-study team attending anesthesiologist available both in the operating room and in the PACU to care for the patient in the event of any potential adverse event. This includes the availability of any resuscitation medications and/or equipment including but not limited to naloxone and emergent airway equipment.

5.6. Data Collection Procedures for Adverse Events. An adverse event would be evident as the study data on pain control, respiratory events, and PONV are collected as per routine standard of care.

5.7. Reporting of Adverse Events. Any adverse event will be reported to the IRB within 7 days as required. Any occurrences of serious adverse events or death will be reported within 24 hours.

6. Statistical Plan

6.1. Sample Size Determination and Sample Size Estimation. Sample size estimations were performed to determine the number of patients required to see a 50% reduction in the patients requiring rescue analgesia between the group receiving fentanyl and the

[figure not shown]
CONFIDENTIAL: This document is the intellectual property of [name] and [name], PhD. Acceptance of this document constitutes the agreement by the recipient that no unpublished information contained herein will be published or disclosed without prior written approval.

group receiving hydromorphone. Each estimation assumed achieving 80% Power, Alpha of 5%, 2 study groups at 1:1 ratio, and 20% attrition (equivalent by study group).

Multiple power curves were calculated. As examples, assuming the proportion using rescue analgesics among patients in the fentanyl study group was 36% compared to a 50% reduction down to 18% for the hydromorphone group, a power analysis comparing independent proportions would require a total sample size of 228 participants. If 50% of the Fentanyl study group utilized rescue analgesics, detecting a 50% reduction down to 25% for the Hydromorphone group, a power analysis comparing independent proportions would require a total sample size of 139 participants (Fig. 1). We selected 300 patients based on an assumed proportion of 0.35 in the fentanyl group requiring rescue opioid analgesia and a goal of 50% reduction in patients requiring analgesia.

CONFIDENTIAL: This document is the intellectual property of [name] and [name], PhD. Acceptance of this document constitutes the agreement by the recipient that no unpublished information contained herein will be published or disclosed without prior written approval.

Figure 1: Sample size estimation curves. P2 = Fentanyl.

6.2. Analysis Plan. De-identified data will be entered into an excel spreadsheet and then SPSS will be used for data analysis. Demographic data will be summarized using descriptive statistics and the two groups will be examined for baseline differences. Descriptive statistics will include proportions, means, and standard deviation to determine statistically significant differences ($p<0.05$). If the differences at baseline are significant, confounders will be addressed using multivariate adjustment techniques. Alpha level 0.05 will be used.

7. Data Handling and Record Keeping

7.1. Confidentiality and Security. The consent forms and all questionnaires will be collected and stored in a locked file drawer in a locked office. Responses to questionnaires will be entered into a password protected computer. All study data will be entered into a database on a password protected computer. Only study team members will have access to the data. All reporting of data will be in the aggregate.

8. Risks, Study Monitoring and Administration

8.1. Monitoring. Studies conducted in the Department of Anesthesiology follow the Washington University Institutional Review Board Policies and Procedures (last revision January 21, 2019). All individuals working on the study are required to read and be familiar with and compliant with the IRB Policies and Procedures. The specific monitoring plan for this investigation is commensurate with the risks and the size and complexity of the investigations planned. The potential risks are attributable to the use of opioids in the perioperative period. Both drugs of interest are standard of care medications and on formulary at SLCH. Thus, the risk of study participation is nearly identical to that incurred with having a tonsillectomy at SLCH, regardless of study participation. Based on the small size and relatively low risk nature of the protocol, the investigating physicians are involved in the monitoring plan. Additionally, a board-certified anesthesiologist practicing in pediatric anesthesia at SCLH who is not a member of the research team will be included in the monitoring of all adverse events. These individuals will review the annual summary

CONFIDENTIAL: This document is the intellectual property of [name] and [name], PhD. Acceptance of this document constitutes the agreement by the recipient that no unpublished information contained herein will be published or disclosed without prior written approval.

of adverse events. All reports of a Serious Adverse Event, or an Unexpected Adverse Event will be reviewed and reported to the IRB. The investigators will follow the requirements for principle investigator reporting requirements as outlined in Section X of the IRB Policies and Procedures.

8.2. Funding and Conflicts of Interest. Departmental funding; an intramural ICTS grant is pending. No conflicts of interest for any of the study team members.

8.3. Study Timetable. The study is expected to start immediately after receiving IRB approval. Data collection will take 24-36 months; analysis another 3-6 months.

9. Publication Plan

Publication in a peer-reviewed medical journal is expected following completion of the data collection and analysis of the results. Presentation at regional and/or national meetings is also anticipated. Establishing best practices for the use of opioids in children is a high priority in pediatric anesthesia, and we anticipate national interest in this research.

10. Management of Intercurrent Events

